#### 14.2.4 Incompatibilities

Ibrutinib is a small molecule administered orally and is primarily metabolized by cytochrome P450 3A4 (CYP3A4). Concomitant use of ibrutinib and strong inducers or inhibitors of CYP3A is contraindicated (see Sections [4.2](#) and [4.3](#)). Please refer to the package insert and PDR for full drug interactions and toxicities.

### 14.3 PREDNISONE

#### 14.3.1 Source, Acquisition and Accountability

Prednisone is a commercially available agent and will be purchased by the CCR and supplied to the participants enrolled on the study by the NIH Clinical Center Pharmacy Department. Please refer to the package insert for additional guidance on drug preparation, handling and storage.

#### 14.3.2 Toxicity

The most commonly reported toxicities have included insomnia; mood, appetite, and skin changes; gastrointestinal problems/pain; and headache, dizziness, and redistribution of body fat. Please refer to the package insert for a complete listing of all toxicities.

#### 14.3.3 Administration Procedures

Prednisone will be administered orally per the drug administration schedule in Section [3.2](#)

#### 14.3.4 Incompatibilities

Please refer to the package insert and PDR for full drug interactions and toxicities.

### 14.4 OBINUTUZUMAB

#### 14.4.1 Source, Acquisition and Accountability

Obinutuzumab is a commercially available agent and will be purchased by the CCR and supplied to the participants enrolled on the study by the NIH Clinical Center Pharmacy Department.

#### 14.4.2 Administration Procedures

Obinutuzumab will be administered by IV on Days 1 and 2 of each 21-day treatment cycle (Cycles 1–6). Premedication will be used to reduce the risk of infusion related reactions (IRRs) as outlined in Section [3.2](#), prior to the obinutuzumab infusion.

Hypotension may occur during obinutuzumab IV infusions. Consider withholding antihypertensive treatments for 12 hours prior to and throughout each obinutuzumab infusion, and for the first hour after administration.

#### 14.4.3 Incompatibilities

No formal drug interaction studies have been performed with obinutuzumab. Please refer to the [package insert](#) and PDR for full drug interactions and toxicities.

### 14.5 LENALIDOMIDE

#### 14.5.1 Source, Acquisition and Accountability

Lenalidomide is a commercially available agent and will be purchased by the CCR and supplied to the Participants enrolled on the study by the NIH Clinical Center Pharmacy Department.

Lenalidomide will be provided in accordance with the Revlimid REMS™ program of Celgene Corporation. Per standard Revlimid REMS™ requirements, all physicians who prescribe lenalidomide for research participants enrolled into this study, and all research participants enrolled into this study, must be registered in, and must comply with all requirements of the Revlimid REMS™ program.

Further information about the Revlimid REMS™ program is available at [www.celgeneriskmanagement.com](http://www.celgeneriskmanagement.com).

Drug will be shipped on a per participant basis by the contract pharmacy to the clinic site for IND studies.

**NOTE:** Prescriptions must be filled within 7 days for individuals of childbearing potential and within 14 days for all other risk categories. Only enough lenalidomide for one cycle of therapy will be supplied to the participant each cycle, unless otherwise agreed to by the investigator/Celgene in advance.

#### 14.5.2 Toxicities

Please refer to the package insert.

#### 14.5.3 Administration procedures

Lenalidomide should be taken orally at about the same time each day. The capsules should not be opened, broken, or chewed. Lenalidomide capsules should be swallowed whole, preferably with water, either with or without food, and may be administered with venetoclax, ibrutinib and prednisone.

Individuals of childbearing potential should not handle or administer lenalidomide unless they are wearing gloves.

If less than 12 hours has elapsed since missing a dose, the participant can take the dose. If more than 12 hours has elapsed since missing a dose at the normal time, the participant should not take the dose, but take the next dose at the normal time on the following day. Do not take 2 doses at the same time.

If a Day 1 (of any cycle) is delayed due to scheduling, instruct the participant that lenalidomide dosing should not be initiated until Day 1 assessments can occur.

#### 14.5.4 Incompatibilities

For participants taking digoxin, periodic monitoring of digoxin plasma levels is recommended due to increased  $C_{max}$  and AUC with concomitant lenalidomide therapy (please see prescribing

information).

Participants taking concomitant therapies such as erythropoietin stimulating agents or estrogen containing therapies, may have an increased risk of venous thromboembolism (please see prescribing information).

Results from human in vitro studies show that lenalidomide is neither metabolized by nor inhibits or induces the cytochrome P450 pathway suggesting that lenalidomide is not likely to cause or be participant to P450-based metabolic drug interactions (please see lenalidomide prescribing information).

Please refer to the [package insert](#) and PDR for full drug interactions and toxicities.

## 16 LIST OF ABBREVIATIONS

Abbreviation	Term
ABC	Activated B-cell
ACAT	Ability to Consent Assessment Team
AE	Adverse Event/Adverse Experience
AESI	Adverse Event/Experience of Special Interest
ALT	Alanine Aminotransferase
ANC	Absolute neutrophil count
ASCT	Autologous stem cell transplantation
AST	Aspartate Aminotransferase
AUC	Area under the curve
BAL	Bronchoalveolar lavage
BTK	Bruton's tyrosine kinase
BTRIS	Biomedical Translational Research Information System
CAP	CT chest, abdomen, and pelvis
CCR	Center for Cancer Research
CDA	Confidential Disclosure Agreement
CFR	Code of Federal Regulations
CI	Confidence Interval
CNS	Central nervous system
CNSL	CNS lymphomas
CONSORT	Consolidated Standards of Reporting Trials
COV	Close-out Visit
CR	Complete Response
CrCl	Creatinine Clearance
CSF	Cerebrospinal fluid
CSR	Clinical Study Report
CRADA	Cooperative Research and Development Agreement
CT	Computed Tomography
CTA	Clinical Trials Agreement
CTCAE	Common Terminology Criteria for Adverse Events
ctDNA	Circulating DNA
DLBCL	Diffuse large B-cell lymphoma
DLT	Dose-limiting toxicity
DS	Double strength
DSMB	Data Safety Monitoring Board (DSMB)
DTA	Data Transfer Agreement
EBV	Epstein Barr Virus
EC	Ethics Committee
eCRF	Electronic Case Report Form
ECOG	Eastern Cooperative Oncology Group
EFS	Event-free survival

Abbreviation	Term
EKG	Electrocardiogram
FDA	Food and Drug Administration
FWA	Federal-Wide Assurance
GCP	Good Clinical Practice
GDS	Genomic Data Sharing
GLP	Good Laboratory Practices
GMP	Good Manufacturing Practices
HBsAg	Hepatitis B surface antigen
HBV	Hepatitis B virus
HBcAb	Hepatitis B core antibody
HBsAb	Hepatitis B surface antibody
HCV	Hepatitis C virus
HCVAb	Hepatitis C antibody
HD-MTX	High dose methotrexate
HHS	Health and Human Services
HIV	Human immunodeficiency virus
IB	Investigator's Brochure
IBC	Institutional Biosafety Committee
ICD/ICF	Informed Consent Document/Form
ICH	International Council for Harmonisation
IMIDs	Immunomodulatory imide drugs
IMV	Interim Monitoring Visit
IND	Investigational New Drug
IOCBP	Individuals of childbearing potential
IPI	International Prognostic Index
IRB	Institutional Review Board
IRBO	Institutional Review Board Office
IRR	Infusion related reactions
IV	Intravenous
LAR	Legally Authorized Representative
LD	Lactate dehydrogenase
LDH	Lactic dehydrogenase
MBL	Monoclonal B-cell lymphocytosis
MGUS	Monoclonal gammopathy of undetermined significance
MRI	Magnetic Resonance Imaging
NCT	National Clinical Trial (number)
NHL	Non-Hodgkin lymphoma
NIH	National Institutes of Health
OHSRP	Office for Human Subjects Research Protections
OHRP	Office for Human Research Protections
OS	Overall survival

Abbreviation	Term
OSRO	Office of Sponsor and Regulatory Oversight
OTT	Oral Targeted Therapy
PCR	Polymerase chain rEACTION
PD	Progressive Disease
PET	Positron Emission Tomography
PFS	Progression-free survival
PI	Principal Investigator
PK	Pharmacokinetic
PCNSL	Primary diffuse large B-cell lymphoma of the CNS
PR	Partial Response
PS	Performance Status
PT	Prothrombin time
PTT	Partial thromboplastin time
QA	Quality Assurance
QC	Quality Control
SAE	Serious Adverse Event/Serious Adverse Experience
SAV	Site Assessment Visit
SCNSL	Aggressive B-cell lymphomas with secondary CNS involvement
SIV	Site Initiation Visit
SD	Stable Disease
SOP	Standard Operating Procedure
TEDDI-R	Ibrutinib with temozolomide, etoposide, liposomal doxorubicin, dexamethasone, and rituximab
TSH	Thyroid stimulating hormone
ULN	Upper limit of normal
US	United States
WBRT	Whole brain radiation
WHO	World Health Organization
VIPOR	Venetoclax, ibrutinib, prednisone, obinutuzumab, lenalidomide
VTE	Venous thromboembolism

## **17 APPENDICES**

### **17.1 APPENDIX A: PERFORMANCE STATUS CRITERIA**

ECOG Performance Status Scale	
Grade	Descriptions
0	Normal activity. Fully active, able to carry on all pre-disease performance without restriction.
1	Symptoms, but ambulatory. Restricted in physically strenuous activity, but ambulatory and able to carry out work of a light or sedentary nature (e.g., light housework, office work).
2	In bed <50% of the time. Ambulatory and capable of all self-care, but unable to carry out any work activities. Up and about more than 50% of waking hours.
3	In bed >50% of the time. Capable of only limited self-care, confined to bed or chair more than 50% of waking hours.
4	100% bedridden. Completely disabled. Cannot carry on any self-care. Totally confined to bed or chair.
5	Dead.

## 17.2 APPENDIX B: CHILD-PUGH SCORE

Measure	1 point	2 points	3 points
Total bilirubin, $\mu$ mol/L (mg/dL)	<34 (<2)	34-50 (2-3)	>50 (>3)
Serum albumin, g/L (g/dL)	>35 (>3.5)	28-35 (2.8-3.5)	<28 (<2.8)
PT INR	<1.7	1.71-2.30	>2.30
Ascites	None	Mild	Moderate to Severe
Hepatic encephalopathy	None	Grade I-II (or suppressed with medication)	Grade III-IV (or refractory)

Points	Class
5-6	A
7-9	B
10-15	C

Source:  
[38], [39]

## 17.3 APPENDIX C: RISK OF FETAL EXPOSURE, PREGNANCY TESTING GUIDELINES AND ACCEPTABLE BIRTH CONTROL METHODS FOR LENALIDOMIDE

### Risks Associated with Pregnancy

The use of lenalidomide in pregnant and nursing individuals has not been studied nor has the effect of lenalidomide on human eggs and sperm. Lenalidomide is structurally related to thalidomide. Thalidomide is a known human teratogenic active substance that causes severe life-threatening birth defects. An embryofetal development study in animals indicates that lenalidomide produced malformations in the offspring of female monkeys who received the drug during pregnancy. The teratogenic effect of lenalidomide in humans cannot be ruled out. Therefore, a risk minimization plan to prevent pregnancy must be observed.

All study participants must be registered into the mandatory Revlimid REMSTM program and be willing and able to comply with the requirements of Revlimid REMSTM.

### Criteria for individuals of childbearing potential (ICBP)

This protocol defines an individual of childbearing potential as a sexually mature individual who: 1) has not undergone a hysterectomy or bilateral oophorectomy or 2) has not been naturally postmenopausal for at least 24 consecutive months (i.e., has had menses at any time in the preceding 24 consecutive months).

The investigator must ensure that:

- Individuals of childbearing potential comply with the conditions for pregnancy risk minimization, including confirmation that she has an adequate level of understanding
- Individuals NOT of childbearing potential acknowledge that they understand the hazards and necessary precautions associated with the use of lenalidomide
- Individuals who can father children taking lenalidomide acknowledge that they understand that traces of lenalidomide have been found in semen, that they understand the potential teratogenic risk if engaged in sexual activity with an individual of childbearing potential or pregnant individual, and that they understand the need for the use of a condom even if they have had a vasectomy, if engaged in sexual activity with an individual of childbearing potential or pregnant individual.

### Contraception

Individuals of childbearing potential (ICBP) enrolled in this protocol must agree to use two reliable forms of contraception simultaneously or to practice complete abstinence from heterosexual intercourse during the following time periods related to this study: 1) for at least 28 days before starting lenalidomide; 2) throughout the entire duration of lenalidomide treatment; 3) during dose interruptions; and 4) for at least 28 days after lenalidomide discontinuation.

The two methods of reliable contraception must include one highly effective method and one additional effective (barrier) method. ICBP must be referred to a qualified provider of contraceptive methods if needed. The following are examples of highly effective and additional effective methods of contraception:

- Highly effective methods:
  - Intrauterine device (IUD)
  - Hormonal (birth control pills, injections, implants)

- Tubal ligation
- Partner's vasectomy
- Additional effective methods:
  - Condom for individuals who can father children
  - Diaphragm
  - Cervical Cap

Implants and levonorgestrel-releasing intrauterine systems are associated with an increased risk of infection at the time of insertion and irregular vaginal bleeding. Prophylactic antibiotics should be considered particularly in participants with neutropenia.

#### Pregnancy Testing

Medically supervised pregnancy tests with a minimum sensitivity of 25 mIU/mL must be performed for individuals of childbearing potential, including individuals of childbearing potential who commit to complete abstinence, as outlined below.

#### **Before starting lenalidomide**

##### *Individuals of Childbearing Potential:*

ICBP must have two negative pregnancy tests (sensitivity of at least 25 mIU/mL) prior to prescribing lenalidomide. The first pregnancy test must be performed within 10–14 days prior to prescribing lenalidomide and the second pregnancy test must be performed within 24 hours prior to prescribing lenalidomide. The participant may not receive lenalidomide until the Investigator has verified that the results of these pregnancy tests are negative.

##### *Individuals Who Can Father Children:*

Must agree to practice complete abstinence or agree to use a condom during sexual contact with individuals who are pregnant or of childbearing potential throughout the entire duration of lenalidomide treatment, during dose interruptions and for at least 28 days following lenalidomide discontinuation, even if he has undergone a successful vasectomy.

#### **During study participation and for 28 days following lenalidomide discontinuation**

##### *Individuals of Childbearing Potential:*

- ICBP with regular or no menstrual cycles must agree to have pregnancy tests weekly for the first 21 days of lenalidomide treatment, including dose interruptions and then every 21 days throughout the remaining duration of lenalidomide treatment, including dose interruptions, at lenalidomide discontinuation, and at Day 30 following lenalidomide discontinuation. If menstrual cycles are irregular, the pregnancy testing must occur weekly for the first 21 days of lenalidomide treatment, including dose interruptions, and then every 14 days throughout the remaining duration of lenalidomide treatment, including dose interruptions, at lenalidomide discontinuation, and at Day 14 and Day 30 following lenalidomide discontinuation.
- At each visit, the Investigator must confirm with the ICBP that they are continuing to use two reliable methods of birth control at each visit during the time that birth control is required.
- If pregnancy or a positive pregnancy test does occur in a study participant, lenalidomide must be immediately discontinued.
- Pregnancy testing and counseling must be performed if a participant misses their period or if their pregnancy test or their menstrual bleeding is abnormal. Lenalidomide treatment must be temporarily discontinued during this evaluation.

- Individuals of childbearing potential must agree to abstain from nursing during study participation and for at least 28 days after lenalidomide discontinuation.

*Individuals Who Can Father Children:*

- Must practice complete abstinence or use a condom during sexual contact with individuals who are pregnant or of childbearing potential throughout the entire duration of lenalidomide treatment, during dose interruptions and for at least 28 days following lenalidomide discontinuation, even if he has undergone a successful vasectomy.
- If pregnancy or a positive pregnancy test does occur in the partner of an individual who can father children during study participation, the investigator must be notified immediately.
- Individuals who can father children should not donate semen or sperm during therapy or for at least 28 days following discontinuation of lenalidomide.

*Additional Precautions:*

- Participants should be instructed never to give lenalidomide to another person.
- Participants should not donate blood during therapy and for at least 28 days following discontinuation of lenalidomide.
- Only enough lenalidomide for one cycle of therapy may be prescribed with each cycle of therapy.
- Any unused lenalidomide must be returned as instructed through the Revlimid REMS™ program.

## 17.4 APPENDIX D: STUDY CALENDAR

### 17.4.1 Screening, Baseline and Treatment

Studies	Screening 		Baseline 	Treatment		
				D1 Cycles 1-6	Weekly Each Cycle	Response Assessment Post C1, C3 and C6
Scheduling Window:	≤28 days	≤14 days	≤14 days	≤1 day for C1 ≤3 days for C2-6	±1 day	≤7 days for C1 and C3 ±7 days for C6
Venetoclax				D1-14		
Lenalidomide				D1-14		
Obinutuzumab				D1, D2		
Ibrutinib				D1-14		
Prednisone				D1-7		
Medical History	X					
Interim History				X		
Confirmation of Diagnosis (any time before treatment initiation, may include biopsy)	X					
Physical and ECOG PS	X			X	X	
Vital Signs and Weight	X			X		X
CBC/diff, platelets	X			X	X	X
Acute Care Panel, Mineral Panel, Hepatic Panel	X			X	X	
LDH				X		X
Uric acid				X		X
Urinalysis				X		
VTE Risk Assessment				X		
PT/ aPTT	X			X		

Studies	Screening 		Baseline 	Treatment		
				D1 Cycles 1-6	Weekly Each Cycle	Response Assessment Post C1, C3 and C6
Scheduling Window:	≤28 days	≤14 days	≤14 days	≤1 day for C1 ≤3 days for C2-6	±1 day	≤7 days for C1 and C3 ±7 days for C6
TSH if abnormal T3 and/or T4			X			
Serum or urine HCG (for IOCBP) 		X		X		
Revlimid REMS® Registration	X					
HIV antibody, HBsAg, HBsAb, HBcAb, HCV Ab 	X			X		
CMV and EBV PCR			X			
TBNK and Quant. IG Panel			X			
MRI brain	X					X
CT scans (C/A/P) 	X					X
 F-FDG-PET Scan brain and body 	X					X (C6 or suspected CR)
Electrocardiogram		X				
Lumbar puncture/Ommaya tap with CSF Testing to include glucose, protein, cell count/differential, cytology, and flow cytometry 		X	X			X (if + at baseline)
Bone marrow biopsy and aspirate 			X			X (C6 if + at baseline)
Ophthalmologic Evaluation 			X			X (C6 if + at baseline)
Symptoms/Adverse Events Assessment 	X		X		X	
Concomitant Medication Review	X		X		X	
Research bloods, saliva/buccal (baseline only), CSF samples (if Ommaya). See Section 5.1.			X	X		

Studies	Screening 		Baseline 	Treatment		
				D1 Cycles 1-6	Weekly Each Cycle	Response Assessment Post C1, C3 and C6
Scheduling Window:	≤28 days	≤14 days	≤14 days	≤1 day for C1 ≤3 days for C2-6	±1 day	≤7 days for C1 and C3 ±7 days for C6
Research Tissues (archival/fresh biopsy) 			X			

---

 Screening evaluations should be performed within 28 days of initiation of protocol therapy, with the following exceptions: Confirmation of diagnosis (no time limit); Serum or urine HCG, Electrocardiogram, and Lumbar puncture/Ommaya tap with glucose, protein, cell count/differential, cytology, and flow cytometry (within 14 days). See additional screening requirements in Section 2.2.

 Baseline evaluations should be performed within 14 days of initiation of protocol therapy, with the following exceptions: Urine and/or serum HCG (within 1 day); Bone marrow aspiration and biopsy (within 3 months), and Research samples (within 7 days). Ophthalmologic evaluation may be performed prior to or after initiation of study therapy (±28 days). Any Screening/Baseline tests performed within the specified time frame for start of treatment do not need to be repeated.

 Urine and/or serum HCG in participants of childbearing potential (within 14 days prior to initiation of Lenalidomide and again within 24 hours prior to initiation of Lenalidomide). See additional pregnancy testing requirements in Section 3.4.2.

 Patients on HBV prophylaxis will have HBV DNA levels obtained monthly during treatment. See additional information in Section 4.1.2.

 CT scans (C/A/P) are to be performed in restaging only if systemic disease present on baseline CT and/or PET imaging.

 PET will be performed at NIH after C6 to confirm CR or may be performed earlier in subjects with suspected CR based on interim imaging. PET body is to be performed in restaging only if systemic disease present on baseline CT and/or PET imaging.

 Performed to confirm disease status. Repeat after Cycles 1, 3 and 6 if CSF was positive for disease at baseline and the previous test result was positive. Once CSF cytology and flow cytometry are negative for disease, further CSF testing need not be repeated unless clinically indicated based on symptoms.

 To be performed within 3 months prior to starting protocol treatment. In follow-up: repeat after Cycle 6 if bone marrow was positive for disease at baseline.

 To be performed ±28 days from protocol treatment initiation. In follow-up: repeat after Cycles 3 and/or 6 if ophthalmologic evaluation was positive for disease at baseline.

 Adverse event evaluation begins immediately after the first dose of study drug and continues throughout the treatment/follow-up portion of the study.

 Archival and/or Fresh Tissue Biopsy for gene expression profiling, mutational analysis, and DNA/RNA sequencing are optional at both baseline and at disease progression.

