### 3.1.1 Study Schema

## 3.2 DRUG ADMINISTRATION

After enrollment participants will proceed to induction therapy. A maximum of 6 cycles of induction therapy will be given every 21 days with the following dosing schedule:

- Obinutuzumab 1000 mg IV rate escalated infusiona on days 1 and 2
- Prednisone 100 mg PO daily days 1-7 (approximately 30-60 minutes prior to obinutuzumab infusion on days 1 and 2)
- Ibrutinib 560 mg PO daily days 1-14
- Lenalidomide 15 mg PO daily days 1-14 (if CrCl > 60 mL/min) or 10 mg PO daily days 1-14 (if CrCl < 60 mL/min but > 40 mL/min)
- Venetoclax 800 mg PO daily on days 1-14
- Acetaminophen 650 mg PO daily on days 1 and 2 (approximately 30-60 minutes prior to Obinutuzumab infusion)
- Diphenhydramine 50 mg PO daily on days 1 and 2 (approximately 30-60 minutes prior to Obinutuzumab infusion)
- Peg-filgrastim 6 mg subcutaneous once on day 8 only

a Obinutuzumab infusion starting at 50 mg/hr with rate increase by 50 mg/hr every 30 minutes as tolerated to a maximum rate of 400 mg/hr. If tolerated, subsequent infusions may start at 100 mg/hr with rate increase by 100 mg/hr every 30 minutes to a maximum rate of 400 mg/hr. Monitor participants closely for signs/symptoms of the infusion reaction and interrupt/discontinue infusion for any signs of a reaction and contact the investigator.

For more details see Section [14](#)

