  - A FCBP with irregular menstruation must have a pregnancy test weekly for the first 21 days and then every 14 days while on lenalidomide therapy (including breaks in therapy), at discontinuation of lenalidomide and at Day 14 (+/-1 day) and at 30 Day safety visit.
- 24-hour urine creatinine clearance (if needed to measure CrCl in cases where serum creatinine >1.5 mg/dl)
- Urinalysis
- Quantitative Immunoglobulin Panel
- EKG to determine eligibility
- Imaging evaluations:
  - CT scans (chest, abdomen, and pelvis); may be adjusted to assess additional known sites of disease
  - Brain MRI
  - F-FDG-PET Scan brain and body (must be performed at NIH only). Additional PET/MRI may be performed as clinically indicated.

These scans (with the exception of F-FDG-PET) may be performed outside of the NIH and the result forwarded to the study team for review at screening or any time during the study. Given that the methodologies utilized are similar across all facilities, no significant variability is expected and there is no anticipation that study data will be affected.

- Lumbar puncture/Ommaya tap for CSF studies including protein, glucose, cell count/differential, cytology, and flow cytometry to determine eligibility and during the study if clinically indicated.
- Bone marrow aspiration/biopsy should be performed within 3 months prior to starting protocol treatment. May be repeated after Cycle 6 if the previous test result was positive or if otherwise clinically indicated.
- Study drug administration schedule- see Section [3.2](#)
- Adverse events and concomitant medication review: Adverse events and concomitant medication will be continuously monitored throughout the study until disease progression

or end of treatment visit. Adverse events that occur beyond 30 days after the last administration will be recorded per [6.1](#).

- Correlative studies: Refer to section [5](#)

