## 5 CORRELATIVE STUDIES FOR RESEARCH

### 5.1 BIOSPECIMEN COLLECTION

Sample	Collection Details*	Time Points	Supervising Laboratory/ Investigator ▲
Blood Samples			
ctDNA	• 2 x 10 mL Streck/BCT tube	• Baseline • At the end of every cycle • At follow-up visit (not at 30 Day Safety visit) • At disease progression	BPC
PBMCs for mutational analysis	• 1 x 8 ml CPTs (sodium heparin)	• Baseline • At the end of every cycle • At disease progression	BPC
Cytokines	• 1 x 8-10 mL RTT	• Baseline • End of treatment visit	BPC
Ibrutinib and Venetoclax PK	• 2 x 2ml GTT (sodium heparin)	• C1D1: ➢ Prior to dose of ibrutinib and venetoclax ➢ 1 hour post ibrutinib and venetoclax (+/-20 min) ➢ 10-18 hours post ibrutinib and venetoclax	BPC
CSF*			
ctDNA	• 3 ml in a sterile syringe	• Baseline • At the end of every cycle • At follow-up visit (not at 30 Day Safety visit) • At disease progression	BPC

Sample	Collection Details*	Time Points	Supervising Laboratory/ Investigator ^
Ibrutinib and Venetoclax PK	
 
0.5 mL in a cryovial supplied by Lymphoma Team Research Nurse
 
	
 
C1D1:                     
 
Prior to dose of ibrutinib and venetoclax
 
1 hour post ibrutinib and venetoclax (+/-20 min)
 
10-18 hours post ibrutinib and venetoclax
 
 
 
	BPC
Other samples			
Archival and/or Fresh Tissue Biopsy for gene expression profiling, mutational analysis, and DNA/RNA sequencing.	
 
FFPE (block or slides);
 
Excision (single or multiple nodes) or core (4-6 passes); placed in formalin/FFPE and media, as appropriate
 
	
 
Baseline (optional)
 
At disease progression (optional)
 
	NCI LP/ [name]
Germline DNA for whole exome sequencing	
 
Blood, Buccal swab, or Saliva 1 x 8 ml CPTs (sodium heparin) for blood
 
	
 
Baseline
 
	BPC

\*CSF studies will only be performed in participants with Ommaya Reservoirs.  
 \*\*Tubes/media may be adjusted at the time of collection based upon materials available or to ensure the best samples are collected for planned analyses.  
 ^The location of specimen processing or analysis may be adjusted with the permission of the PI or laboratory investigator.

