## 10 STATISTICAL CONSIDERATIONS

### 10.1 OBJECTIVES AND ENDPOINTS

OBJECTIVES	ENDPOINTS	JUSTIFICATION FOR ENDPOINTS
Primary		
To determine the safety and feasibility of VIPOR in primary DLBCL of the CNS (PCNSL) and secondary CNS lymphoma (SCNSL)	The fraction of participants who completed at least 2 cycles of VIPOR therapy without stopping due to toxicity.	Standard endpoint for cancer clinical trials.
Secondary		
To determine the overall response rate (ORR) of up to 6 cycles of VIPOR in CNSL	ORR = CR+PR- assessed after cycles 3 and 6	Standard endpoints for cancer clinical trials

OBJECTIVES	ENDPOINTS	JUSTIFICATION FOR ENDPOINTS
To determine the complete response (CR) rate of up to 6 cycles of VIPOR in CNSL	CR- The rate of complete response by Lugano, assessed after cycles 3 and 6	Standard endpoints for cancer clinical trials, CR is the endpoint chosen because with these diseases, PR is not relevant as all participants will relapse.
To determine the duration of response (DOR) after VIPOR in CNSL	Duration of response (DOR)- measured from the time of first response until the first date that recurrent or progressive disease is objectively documented, death, or, in the absence of PD, date of last assessment (10 years post-treatment)	Standard endpoints for cancer clinical trials, success of regimens will be determined by these endpoints.
To estimate the progression-free survival (PFS) after VIPOR in CNSL	Progression free survival (PFS) – calculated up to 10 years post-treatment	Standard endpoints for cancer clinical trials, success of regimens will be determined by these endpoints.
To assess overall survival (OS) after VIPOR in CNSL	Overall survival (OS)- calculated up to 10 years post-treatment	Standard endpoints for cancer clinical trials, success of regimens will be determined by these endpoints.
Tertiary/Exploratory		
To perform comprehensive molecular profiling of CNSL tumors and explore correlations with clinical response	Each of these will be evaluated using descriptive methods and reported as exploratory results. If any statistical tests are performed in these analyses, the results will be presented without adjustment for multiple comparisons but reported in the context of the number of tests performed. See Section 5.1 for collection timepoints.	Exploratory analysis
To genotype circulating tumor DNA (ctDNA) from plasma and CSF and correlate to tissue genotyping		
To study cytokine changes across VIPOR therapy		

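### Scheduled CSF testing may lapse after the first negative result, so a later CR can rest on a carried-forward CSF sample (up to about 17 weeks old after cycle 6, without delays)

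*Combined protocol and SAP*

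**What the plan says.** In the Study Calendar (Appendix D, section 17.4.1), the CSF row under the response assessments after cycles 1, 3 and 6 reads "X (if + at baseline" (closing bracket not shown). The row label carries footnote marker 7. The footnote sets two conditions: "Repeat after Cycles 1, 3 and 6 if CSF was positive for disease at baseline and the previous test result was positive". It then adds: "Once CSF cytology and flow cytometry are negative for disease, further CSF testing need not be repeated unless clinically indicated based on symptoms".

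Section 3.4.2 describes the same procedure differently. CSF is examined "to determine eligibility and during the study if clinically indicated", and no scheduled repeat is mentioned.

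The response rules that use the result are these:

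- Section 6.3.1 (PCNSL): the CR row requires negative CSF cytology, and recurrent or positive cytology is listed under PD. No maximum age for the sample is given.
- Section 6.3.2 (SCNSL): CSF is not named. CR requires that all detectable disease has gone.
- Section 10.1: the CR endpoint is "The rate of complete response by Lugano, assessed after cycles 3 and 6", and ORR has the same timing.

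For the research samples, section 5.1 states that "CSF studies will only be performed in participants with Ommaya Reservoirs". In those participants 3 ml of CSF is drawn for ctDNA at baseline, at the end of every cycle, at follow-up visits and at progression.

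**The concern.** Whether CSF is measured again depends on the last result. A participant who remains CSF-positive keeps being tested at each response assessment. One who has cleared need not be, although CR is judged later and, in PCNSL, requires negative CSF at that point.

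The exposed participant is CSF-positive at baseline, clears after cycle 1, and reaches CR on imaging only at the cycle 3 or cycle 6 assessment. If the CSF relapsed in between without symptoms and without suspicious imaging, the old negative would stand and the participant would be counted as CR. The error has one direction: an unrepeated negative can hide a relapse but cannot create one, so the CR rate and ORR can only be raised.

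The protocol is stricter about another site. In section 6.3.2, a radiological CR in a participant with marrow involvement at baseline is classed as PR if the marrow was not examined after treatment. No comparable rule covers CSF.

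**Working it through.** The plan states no figure for the age of the CSF sample, so there is none to reproduce. The check is calendar arithmetic.

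**Inputs**

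- Section 3.2: "A maximum of 6 cycles of induction therapy will be given every 21 days". Study day = 21 x (cycle - 1) + day of cycle.
- Section 3.4.3.1: the assessments after cycles 1 and 3 fall within 7 days before day 1 of the next cycle; the assessment after cycle 6 falls on cycle 6 day 21, plus or minus 7 days.
- Section 3.3.1: a cycle start may be delayed by up to 6 weeks (42 days).

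**Assessment windows, no delays**

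- After cycle 1: cycle 2 day 1 = 21 x 1 + 1 = day 22, so days 15-22.
- After cycle 3: cycle 4 day 1 = 21 x 3 + 1 = day 64, so days 57-64.
- After cycle 6: cycle 6 day 21 = 21 x 5 + 21 = day 126, so days 119-133.

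**Age of the CSF sample behind the response call** (day of assessment minus day of last negative sample)

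| Last CSF sample | Response call | Shortest | Longest | Weeks |
|---|---|---|---|---|
| After cycle 1 | After cycle 3 | 57 - 22 = 35 days | 64 - 15 = 49 days | 5.0-7.0 |
| After cycle 1 | After cycle 6 | 119 - 22 = 97 days | 133 - 15 = 118 days | 13.9-16.9 |
| After cycle 3 | After cycle 6 | 119 - 64 = 55 days | 133 - 57 = 76 days | 7.9-10.9 |

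**With permitted delays.** Each maximal delay after the sample adds 42 days. One delay gives at most 118 + 42 = 160 days (22.9 weeks). Maximal delays at cycles 3, 4, 5 and 6 would give 118 + 4 x 42 = 286 days (40.9 weeks). About 17 weeks is therefore the longest age on an undelayed schedule, not an absolute ceiling.

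**Size per participant.** One reclassified participant moves the CR rate by 100/n points. If all 10 planned participants are evaluable for response, that is 100/10 = 10 points. If all 12 places left under the accrual ceiling (16 - 4) are evaluable, it is 100/12 = 8.3 points. It is more than 10 points if fewer than 10 are evaluable. This is a unit of change and not an expected bias: the documents give no rate of CSF involvement in this population, of CSF clearance or of silent CSF relapse.

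**With CSF read at the assessment itself.** Sample and imaging would share one window, at most 64 - 57 = 7 days apart after cycle 3 and 133 - 119 = 14 days apart after cycle 6.

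**The case against.** Several points on the other side stand, and they limit the issue.

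- A reader might infer that the calendar cell and footnote 7 contradict each other. They do not: the row carries marker 7, so the footnote narrows the cell, as footnote 5 narrows the CT row. The real mismatch is with section 3.4.2, and even there section 3.4 defers to the calendar. That is a wording repair.
- A reader might infer that a cleared participant is never retested without symptoms. The footnote is permissive, and section 3.4.3.2 requires CSF with cytology and flow whenever progression is suspected or confirmed. Suspicion can come from imaging, and brain MRI is scheduled at each response assessment. The gap is a relapse that is silent both clinically and on imaging.
- Under best overall response (section 6.3.7), a CR met with a CSF sample negative at the same time stands whatever happens later. This does not protect a CR first reached on imaging after the CSF has stopped being tested.
- A reader might infer that PFS is inflated as well. After treatment, section 17.4.2 schedules no clinical CSF test before progression for anyone, so footnote 7 leaves most of the PFS window unchanged. During treatment it could at most delay the dating of an event.
- Inclusion criterion 2.1.1.3 requires disease evaluable by examination or imaging, so CSF is not the only evaluable site in any eligible participant.
- Sparing an invasive test after clearance is a defensible choice. An Ommaya reservoir is not required (section 3.1), and section 12.4.1.7 lists bleeding and brainstem herniation among the risks of lumbar puncture. This is a good reason not to ask for extra lumbar punctures.

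What remains is that no rule says whether a carried-forward negative CSF may support CR.

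**Conclusion.** The concern holds as a minor, cheap improvement to secondary endpoints. Without delays, a CR after cycle 3 can rest on CSF 5-7 weeks old, and a CR after cycle 6 on CSF 14-17 weeks old (97-118 days); permitted delays lengthen both. Any resulting error raises the CR rate and ORR. The number of participants affected cannot be computed from the documents and may be zero.

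This rests on three assumptions. CSF was positive at baseline and first negative after cycle 1. Imaging first met CR at a later assessment. Responses are classified by section 6.3, as section 10.3.2 states, although section 10.1 names Lugano for CR. The dependence on CSF is explicit for PCNSL; for SCNSL it is indirect, through the general requirement that no detectable disease remains.

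A reader might infer that the trial's conclusion is at risk. The documents do not support that. The primary endpoint and the rule of 7 successes in 10 (sections 10.2 and 10.4.2) do not use CSF, and section 10.4.3 reports ORR and CR with confidence intervals and no success threshold.

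**What to change.** 1. For participants who were CSF-positive at baseline and have an Ommaya reservoir, run cytology and flow cytometry at the CSF draws already made at the end of cycles 3 and 6, provided the volume is adequate. Section 5.1 specifies 3 ml for ctDNA and does not show that this also covers cytology and flow.
2. For all other participants who were CSF-positive at baseline, require no additional lumbar puncture. Flag any CR that relies on a carried-forward negative CSF. In section 10.4.3, add that the CR rate and ORR are reported with and without those cases. The simplest form of the second figure keeps the denominator and counts the flagged cases as not confirmed.
3. Reconcile the CSF wording in section 3.4.2 with calendar footnote 7.

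The cost is a little more laboratory and analysis work, possibly slightly more CSF per draw, one footnote and one analysis sentence. The reported CR rate may be slightly lower.
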